4.2.3 Rationale for Endpoints

4.2.3.1 Efficacy Endpoints

Historically, doxorubicin has been used in combination with Ifosfamide as front line therapy for patients with advanced sarcomas. However, the EORTC randomized patients to receive single agent doxorubicin or the combination with ifosfamide. Although the combination did lead to improved progression free survival, the trial found no significant

change in overall survival associated with the combination therapy and significantly increased toxicity associated with the combination. This study established single agent doxorubicin as standard front line therapy for patients with advanced sarcoma. In patients with advanced STS, doxorubicin has a response rate of 15% and results in a median progression free survival (PFS) of approximately 4.6 months (Santoro, Tursz et al. 1995, Judson 2013, Gelderblom, Blay et al. 2014). The primary objective of the phase II design is to compare the objective response rate (ORR) with historical rates.

4.2.3.2 Biomarker Research

We tested over 80 sarcoma tumors including both LMS and SS for expression of PD-L1 and PD-1; we found some degree of PD-1 expressing cells in over 90% of tumors examined. Detectable PD-L1 was seen in a subset of each sarcoma subtype tested, including n=11 (58%) of LMS and n=7 (47%) SS. PD-1 expressing lymphocytes were also seen in a majority of tumors including n=16 (84%) LMS and n=15 (100%) SS. High (4+) or very high (5+) PD-L1 expression was seen in 10 sarcoma including 3 LMS (**Figure 2 A and B**). Seven tumors had high or very high PD-1 expression including one SS, and two LMS. In contrast, even though 100% of the SS tumors had some PD-1 expression, none of the SS tumors had either 4+ or 5+ PD-1 expression. Only n=4 (27%) of SS tumors had >2+ expression for PD-L1. Higher-grade tumors were associated with higher levels of both PD-L1 ($p = 0.03$) and PD-1 expression ($p = 0.05$).

[figure not shown]

Fig.: A) High PD-1 staining in a high grade, metastatic sarcoma. B) Profuse membranous tumor cell staining for PD-L1 in a leiomyosarcoma tumor. C) Graph showing intensity of staining for individual sarcoma subtypes.

5.0 METHODOLOGY

5.1 Entry Criteria

This trial is designed for both male and female patients ≥ 18 years of age with unresectable sarcoma not amenable to surgery or radiation with curative intent and an ECOG performance status of 0 or 1. We expect 9 patients will be treated on the phase I dose escalation portion of the trial (it is possible as few as 6 and as many as 12 patients could be treated on the phase I portion) and 35 additional patients will be treated on the phase II expansion. All patients meeting the eligibility criterion will be considered for enrollment. No exceptions to eligibility will be granted.

5.1.1 Diagnosis/Condition for Entry into the Trial

As is the standard practice in the Seattle Cancer Care Alliance Sarcoma Clinic, all patients must have had their pathology reviewed at the University of Washington sarcoma clinic. Certain sarcoma subtypes such as Osteosarcoma and Ewings sarcoma almost always receive anthracyclines in combination with other agents as part of their standard of care and therefore it would not make sense for those patients to participate in this study. Both patients with soft tissue sarcoma as well as patients with bone sarcomas (for example chondrosarcoma, leiomyosarcoma of the bone etc.) may be allowed on this trial as this is an anatomic distinction rather than a biologic or immunologic distinction.

5.1.2 Subject Inclusion Criteria

In order to be eligible for participation in this trial, the subject must:

1. Be willing and able to provide written informed consent/assent for the trial.
2. Be ≥ 18 years of age on day of signing informed consent.
3. Have measurable disease based on RECIST 1.1.
4. Have metastatic or unresectable sarcoma.
5. Have a performance status of 0 to 1 on the ECOG Performance Scale.
6. Demonstrate adequate organ function as defined in Table 1, all screening labs should be performed within 10 days of treatment initiation.

Table 1: Adequate Organ Function Laboratory Values

System	Laboratory Value
Hematological	
Absolute neutrophil count (ANC)	$\geq 1,500$ /mcL

Platelets	$\geq 100,000$ / mL
Hemoglobin	≥ 9 g/dL or ≥ 5.6 mmol/L without transfusion or EPO dependency (within 7 days of assessment)
Renal	
Serum creatinine OR Measured or calculated ^a creatinine clearance (GFR can also be used in place of creatinine or CrCl)	≤ 1.5 X upper limit of normal (ULN) OR ≥ 60 mL/min for subject with creatinine levels > 1.5 X institutional ULN
Hepatic	
Serum total bilirubin	≤ 1.5 X ULN OR Direct bilirubin \leq ULN for subjects with total bilirubin levels > 1.5 ULN
AST (SGOT) and ALT (SGPT)	≤ 2.5 X ULN OR ≤ 5 X ULN for subjects with liver metastases
Albumin	≥ 2.5 mg/dL
Coagulation	
International Normalized Ratio (INR) or Prothrombin Time (PT)	≤ 1.5 X ULN unless subject is receiving anticoagulant therapy as long as PT or PTT is within therapeutic range of intended use of anticoagulants
Activated Partial Thromboplastin Time (aPTT)	≤ 1.5 X ULN unless subject is receiving anticoagulant therapy as long as PT or PTT is within therapeutic range of intended use of anticoagulants
^a Creatinine clearance should be calculated per institutional standard.	

7. Female subject of childbearing potential should have a negative urine or serum pregnancy within 72 hours prior to receiving the first dose of study medication. If the urine test is positive or cannot be confirmed as negative, a serum pregnancy test will be required.
8. Female subjects of childbearing potential should be willing to use 2 methods of birth control or be surgically sterile, or abstain from heterosexual activity for the course of the study through 120 days after the last dose of study medication (Reference Section 5.7.2). Subjects of childbearing potential are those who have not been surgically sterilized or have not been free from menses for > 1 year.
9. Male subjects should agree to use an adequate method of contraception starting with the first dose of study therapy through 120 days after the last dose of study therapy.
10. Ejection Fraction >45% by either MUGA scan or echocardiogram.

5.1.3 Subject Exclusion Criteria

The subject must be excluded from participating in the trial if the subject:

1. Has prior treatment using an anthracycline.
2. Has one of the following sarcoma subtypes where combining anthracyclines with other chemotherapies is established as the standard of care: Osteosarcoma, Ewings sarcoma, Embryonal Rhabdomyosarcoma, Alveolar Rhabdomyosarcoma.
3. Is currently participating and receiving study therapy or has participated in a study of an investigational agent and received study therapy or used an investigational device within 4 weeks of the first dose of treatment.
4. Has a diagnosis of immunodeficiency or is receiving systemic steroid therapy or any other form of immunosuppressive therapy within 7 days prior to the first dose of trial treatment.
5. Has a known history of active TB (Bacillus Tuberculosis)
6. Hypersensitivity to pembrolizumab or any of its excipients.
7. Has had a prior anti-cancer monoclonal antibody (mAb) within 4 weeks prior to study Day 1 or who has not recovered (i.e., \leq Grade 1 or at baseline) from adverse events due to agents administered more than 4 weeks earlier.
8. Has had prior chemotherapy, targeted small molecule therapy, or radiation therapy within 2 weeks prior to study Day 1 or who has not recovered (i.e., \leq Grade 1 or at baseline) from adverse events due to a previously administered agent.
 - Note: Subjects with \leq Grade 2 neuropathy are an exception to this criterion and may qualify for the study.
 - Note: If subject received major surgery, they must have recovered adequately from the toxicity and/or complications from the intervention prior to starting therapy.
9. Has a known additional malignancy that is progressing or requires active treatment. Exceptions include basal cell carcinoma of the skin or squamous cell carcinoma of the skin that has undergone potentially curative therapy or in situ cervical cancer.
10. Has known active central nervous system (CNS) metastases and/or carcinomatous meningitis. Subjects with previously treated brain metastases may participate provided they are stable (without evidence of progression by imaging for at least four weeks prior to the first dose of trial treatment and any neurologic symptoms have returned to baseline), have no evidence of new or enlarging brain metastases, and are not using steroids for at least 7 days prior to trial treatment. This exception does not include carcinomatous meningitis which is excluded regardless of clinical stability.
11. Has active autoimmune disease that has required systemic treatment in the past 2 years (i.e. with use of disease modifying agents, corticosteroids or immunosuppressive drugs). Replacement therapy (eg., thyroxine, insulin, or

physiologic corticosteroid replacement therapy for adrenal or pituitary insufficiency, etc.) is not considered a form of systemic treatment.

12. Has known history of, or any evidence of active, non-infectious pneumonitis.
13. Has an active infection requiring systemic therapy.
14. Has a history or current evidence of any condition, therapy, or laboratory abnormality that might confound the results of the trial, interfere with the subject's participation for the full duration of the trial, or is not in the best interest of the subject to participate, in the opinion of the treating investigator.
15. Has known psychiatric or substance abuse disorders that would interfere with cooperation with the requirements of the trial.
16. Is pregnant or breastfeeding, or expecting to conceive or father children within the projected duration of the trial, starting with the pre-screening or screening visit through 120 days after the last dose of trial treatment.
17. Has received prior therapy with an anti-PD-1, anti-PD-L1, anti-PD-L2 agent or anti-CTLA4.
18. Has a known history of Human Immunodeficiency Virus (HIV) (HIV 1/2 antibodies).
19. Has known active Hepatitis B (e.g., HBsAg reactive) or Hepatitis C (e.g., HCV RNA [qualitative] is detected).
20. Has received a live vaccine within 30 days of planned start of study therapy.

Note: Seasonal influenza vaccines for injection are generally inactivated flu vaccines and are allowed; however intranasal influenza vaccines (e.g., Flu-Mist®) are live attenuated vaccines, and are not allowed.

5.2 Trial Treatments

The treatment to be used in this trial is outlined below in Table 2

Table 2 Trial Treatment

Drug	Dose/ Potency	Dose Frequency	Route of Administration	Regimen/ Treatment Period	Use
Pembrolizumab	200 mg	Q3W	IV infusion	Day 1 of each 3 week cycle	Experimental
Doxorubicin	45 or 75	Q3W	IV infusion	Day 1 of	Standard

Drug	Dose/ Potency	Dose Frequency	Route of Administration	Regimen/ Treatment Period	Use
	mg/m ²			each 3 week cycle	

All trial treatments will be administered on an outpatient basis.

Pembrolizumab will be administered as a 30 minute IV infusion. However, given the variability of infusion pumps, a window of -5 minutes and +10 minutes will be permitted (i.e., infusion time is 30 minutes: -5 min/+10 min).

A Procedures Manual will contain specific instructions for Pembrolizumab dose calculation, reconstitution, preparation of the infusion fluid, and administration.

Anti-emetics given to prevent and treat doxorubicin associated nausea and vomiting may be given according to the standard of care at the discretion of the treating clinician with the exception that corticosteroids are not recommended as their immunosuppressive effects may impact the efficacy of Pembrolizumab. While steroids are discouraged, they are not absolutely forbidden as there could be an individual situation where the benefits would be worthwhile (e.g. a specific case of very severe and refractory nausea).

As stated in **Section 2.5**, a dose limiting toxicity (DLT) will be defined as a possibly-related, unexpected SAE of grade 3 or higher or any adverse event at least possibly related to either agent requiring discontinuation of either drug.

5.2.1.1 Dose Selection

The rationale for selection of doses to be used in this trial is provided in Section 4.0 – Background and Rationale.

Details on preparation and administration of Pembrolizumab are provided in the Pharmacy Manual.

If a toxicity is clearly attributable to only one drug, the other may be continued per protocol. If a toxicity is clearly attributable to one agent and the dose adjustment or drug withdrawal is not required by the protocol, the treating physician may have the discretion to make dose adjustments as dictated by their clinical judgement.

5.2.1.2 Dose Modification of Pembrolizumab

AEs associated with pembrolizumab exposure may represent an immunologic etiology. These immune-related AEs (irAEs) may occur shortly after the first dose or several months after the last dose of pembrolizumab treatment and may affect more than one body system simultaneously. Therefore, early recognition and initiation of treatment is critical to reduce complications. Based on existing clinical study data, most irAEs were reversible and could be managed with interruptions of pembrolizumab, administration of corticosteroids and/or other supportive care. For suspected irAEs, ensure adequate evaluation to confirm etiology or exclude other causes. Additional procedures or tests such as bronchoscopy, endoscopy, skin biopsy may be included as part of the evaluation. Based on the severity of irAEs, withhold or permanently discontinue pembrolizumab and administer corticosteroids. Dose modification and toxicity management guidelines for irAEs associated with pembrolizumab are provided in

Table

3.

Table 3 Dose modification and toxicity management guidelines for immune-related AEs associated with pembrolizumab

General instructions:				

 1. Corticosteroid taper should be initiated upon AE improving to Grade 1 or less and continue to taper over at least 4 weeks. 2. For situations where pembrolizumab has been withheld, pembrolizumab can be resumed after AE has been reduced to Grade 1 or 0 and corticosteroid has been tapered. Pembrolizumab should be permanently discontinued if AE does not resolve within 12 weeks of last dose or corticosteroids cannot be reduced to ≤ 10 mg prednisone or equivalent per day within 12 weeks. 3. For severe and life-threatening irAEs, IV corticosteroid should be initiated first followed by oral steroid. Other immunosuppressive treatment should be initiated if irAEs cannot be controlled by corticosteroids. 				
Immune-related AEs	Toxicity grade or conditions (CTCAEv4.0)	Action taken to pembrolizumab	irAE management with corticosteroid and/or other therapies	Monitor and follow-up
Pneumonitis	Grade 2	Withhold	
 • Administer corticosteroids (initial dose of 1-2 mg/kg prednisone or equivalent) followed by taper 	
 • Monitor participants for signs and symptoms of pneumonitis • Evaluate participants with suspected pneumonitis with radiographic imaging and initiate corticosteroid treatment • Add prophylactic antibiotics for opportunistic infections
	Grade 3 or 4, or recurrent Grade 2	Permanently discontinue		
Diarrhea / Colitis	Grade 2 or 3	Withhold	
 • Administer corticosteroids (initial dose of 1-2 mg/kg prednisone or equivalent) followed by taper 	
 • Monitor participants for signs and symptoms of enterocolitis (ie, diarrhea, abdominal pain, blood or mucus in stool with or without fever) and of bowel perforation (ie, peritoneal signs and ileus). • Participants with \geqGrade 2 diarrhea suspecting colitis should consider GI consultation and performing endoscopy to rule out colitis. • Participants with diarrhea/colitis should be advised to drink liberal quantities of clear fluids. If sufficient oral fluid intake is not feasible, fluid and electrolytes should be substituted via IV infusion.
	Grade 4	Permanently discontinue		

AST / ALT elevation or Increased bilirubin	Grade 2	Withhold	
 Administer corticosteroids (initial dose of 0.5- 1 mg/kg prednisone or equivalent) followed by taper 	
 Monitor with liver function tests (consider weekly or more frequently until liver enzyme value returned to baseline or is stable)
	Grade 3 or 4	Permanently discontinue	
 Administer corticosteroids (initial dose of 1-2 mg/kg prednisone or equivalent) followed by taper 	
Type 1 diabetes mellitus (T1DM) or Hyperglycemia	Newly onset T1DM or Grade 3 or 4 hyperglycemia associated with evidence of β -cell failure	Withhold	
 Initiate insulin replacement therapy for participants with T1DM Administer anti-hyperglycemic in participants with hyperglycemia 	
 Monitor participants for hyperglycemia or other signs and symptoms of diabetes.
Hypophysitis	Grade 2	Withhold	
 Administer corticosteroids and initiate hormonal replacements as clinically indicated. 	
 Monitor for signs and symptoms of hypophysitis (including hypopituitarism and adrenal insufficiency)
	Grade 3 or 4	Withhold or permanently discontinue ¹		
Hyperthyroidism	Grade 2	Continue	
 Treat with non-selective beta-blockers (eg, propranolol) or thionamides as appropriate 	
 Monitor for signs and symptoms of thyroid disorders.
	Grade 3 or 4	Withhold or permanently discontinue ¹		
Hypothyroidism	Grade 2-4	Continue	
 Initiate thyroid replacement hormones (eg, levothyroxine or liothyronine) per standard of care 	
 Monitor for signs and symptoms of thyroid disorders.
Nephritis and Renal dysfunction	Grade 2	Withhold	
 Administer corticosteroids (prednisone 1-2 mg/kg or equivalent) followed by taper. 	
 Monitor changes of renal function
	Grade 3 or 4	Permanently discontinue		
Myocarditis	Grade 1 or 2	Withhold	
 Based on severity of AE administer corticosteroids 	
 Ensure adequate evaluation to confirm etiology and/or exclude other causes
	Grade 3 or 4	Permanently discontinue		

All other immune-related AEs	Intolerable/ persistent Grade 2	Withhold	
 Based on type and severity of AE administer corticosteroids 	
 Ensure adequate evaluation to confirm etiology and/or exclude other causes
	Grade 3	Withhold or discontinue based on the type of event. Events that require discontinuation include and not limited to: Gullain-Barre Syndrome, encephalitis		
	Grade 4 or recurrent Grade 3	Permanently discontinue		

1. Withhold or permanently discontinue pembrolizumab is at the discretion of the investigator or treating physician.
 
NOTE: For participants with Grade 3 or 4 immune-related endocrinopathy where withhold of pembrolizumab is required, pembrolizumab may be resumed when AE resolves to \leqGrade 2 and is controlled with hormonal replacement therapy or achieved metabolic control (in case of T1DM).
				

Dose modification and toxicity management of infusion-reactions related to pembrolizumab

Pembrolizumab may cause severe or life threatening infusion-reactions including severe hypersensitivity or anaphylaxis. Signs and symptoms usually develop during or shortly after drug infusion and generally resolve completely within 24 hours of completion of infusion. Dose modification and toxicity management guidelines on pembrolizumab associated infusion reaction are provided in Table 4.

Table 4 Pembrolizumab Infusion Reaction Dose modification and Treatment Guidelines

NCI CTCAE Grade	Treatment	Premedication at Subsequent Dosing
Grade 1 Mild reaction; infusion interruption not indicated; intervention not indicated	Increase monitoring of vital signs as medically indicated until the participant is deemed medically stable in the opinion of the investigator.	None
Grade 2 Requires therapy or infusion interruption but responds promptly to symptomatic treatment (e.g., antihistamines, NSAIDs, narcotics, IV fluids); prophylactic medications indicated for ≤ 4 hrs	
Stop Infusion. Additional appropriate medical therapy may include but is not limited to: IV fluids Antihistamines NSAIDs Acetaminophen Narcotics
 
Increase monitoring of vital signs as medically indicated until the participant is deemed medically stable in the opinion of the investigator. If symptoms resolve within 1 hour of stopping drug infusion, the infusion may be restarted at 50% of the original infusion rate (e.g. from 100 mL/hr to 50 mL/hr). Otherwise dosing will be held until symptoms resolve and the participant should be premedicated for the next scheduled dose.
 
Participants who develop Grade 2 toxicity despite adequate premedication should be permanently discontinued from further study drug treatment
	Participant may be premedicated 1.5h (\pm 30 minutes) prior to infusion of _____ with: Diphenhydramine 50 mg po (or equivalent dose of antihistamine). Acetaminophen 500-1000 mg po (or equivalent dose of analgesic).


Grades 3 or 4 Grade 3: Prolonged (i.e., not rapidly responsive to symptomatic medication and/or brief interruption of infusion); recurrence of symptoms following initial improvement; hospitalization indicated for other clinical sequelae (e.g., renal impairment, pulmonary infiltrates) Grade 4: Life-threatening; pressor or ventilatory support indicated
	
Stop Infusion. Additional appropriate medical therapy may include but is not limited to: Epinephrine** IV fluids Antihistamines NSAIDs Acetaminophen Narcotics Oxygen Pressors Corticosteroids Increase monitoring of vital signs as medically indicated until the participant is deemed medically stable in the opinion of the investigator. Hospitalization may be indicated. **In cases of anaphylaxis, epinephrine should be used immediately. Participant is permanently discontinued from further study drug treatment.
	
No subsequent dosing

Appropriate resuscitation equipment should be available at the bedside and a physician readily available during the period of drug administration. For further information, please refer to the Common Terminology Criteria for Adverse Events v4.0 (CTCAE) at http://ctep.cancer.gov
		

Other allowed dose interruption for pembrolizumab

Pembrolizumab may be interrupted for situations other than treatment-related AEs such as medical / surgical events or logistical reasons not related to study therapy. Participants should be placed back on study therapy within 3 weeks of the scheduled interruption, unless otherwise discussed with the Sponsor. The reason for interruption should be documented in the patient's study record.

5.2.1.3 Dose Modification of Doxorubicin

Doxorubicin is a cytotoxic chemotherapy that has a well-defined safety profile and will be given as per the standard of care. Doxorubicin will not be given while a patient's ANC is < 1000 cells/m³ or if the platelet count is <75,000 cells/m³. When necessary, the next treatment cycle should be delayed until these counts have recovered to these levels. Transfusions of red blood cells and platelets are permitted as clinically indicated. If a patient has a grade 3 febrile neutropenia, doxorubicin should be reduced to approximately 75% of the previous dose (first to 60mg/m² then to 45 mg/m²). Dose reductions of doxorubicin are also required for patients having Grade 4 neutropenia lasting more than 1 week. For patients with grade 3 febrile neutropenia or grade 4 neutropenia without fever lasting less than a week, dose reduction may be made at the discretion of the treating physician. Patients with grade 3 fatigue and/or malaise, may have one dose reduction at the discretion of their treating physician.

Patients may not have more than 2 dose reductions of doxorubicin, and must come off doxorubicin should they continue to have prolonged cytopenias (>21 days) after their second dose reduction. If these patients are responding they may stay on Pembrolizumab as a single agent until progression.

LFT abnormalities may also necessitate a dose reduction. For a bilirubin 1.2-1.5, dose reduction may be made at the discretion of the treating clinician. For bilirubin 1.5 -3, 50% dose reduction. For bilirubin 3.0-5.0, give no more than 25% of the prior dose and consider delaying the next cycle.

EKG's will be collected periodically while a patient is receiving doxorubicin and any other times as the treating clinician deems necessary (see section 6.1). If clinically significant findings are observed on EKG, they should be evaluated as seen as appropriate by the treating clinician. An echocardiogram or MUGA scan will be performed prior to starting therapy for all patients. Should a second echocardiogram or MUGA be performed (this is required for patients on the phase I portion of the study), a drop in ejection fraction by more than 15% or to a total ejection fraction of less than 40% means that doxorubicin should be discontinued. While cardiac toxicity is an expected toxicity of doxorubicin, these events should be explicitly pointed out to the DSMB as frequent or severe occurrences could raise the possibility that pembrolizumab is worsening doxorubicin mediated cardiac toxicity.

Dose delays of doxorubicin may be permitted for up to 3 weeks with PI approval for medical reasons not otherwise outlined in this section. The reason and length of the delay should be discussed with PI during the approval process.

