2.0 TRIAL DESIGN

2.1 Introduction

This is a Phase I/II, non-randomized, open-label, interventional study of Pembrolizumab combined with doxorubicin for patients with advanced sarcoma. Most patients will receive this as front line therapy. As a rule, the trial is generally inclusive for most sarcoma subtypes. However, it excludes patients with prior anthracycline treatment. Patients with Ewings Sarcoma, Osteosarcoma, and some Rhabdomyosarcomas are excluded as these histologic sarcoma subtypes have well-established, evidence-based treatment paradigms combining anthracyclines with other chemotherapy.

The Phase I stage will evaluate two dose levels of doxorubicin (45 and 75 mg/m²) combined with Pembrolizumab. The 75 mg/m² doxorubicin dose is widely considered standard of care for sarcoma, as is being used as the “control” arm for recent and on-going phase III trials (NCT02451943) (Judson, Verweij et al. 2014). All patients will receive Pembrolizumab at the flat dose of 200 mg given intravenously every 3 weeks. Unless serious adverse events are observed, the Phase II expansion will combine the 75 mg/m² dose of doxorubicin with Pembrolizumab.

The phase II portion will use a two stage design treating an initial 20 patients with the combination of Doxorubicin and Pembrolizumab. If two or more objective responses are seen (either complete or partial responses), an additional 15 patients will be treated for a total of 35 patients. In summary, we expect that 44 patients will be treated on the trial (9 in the phase I portion and 35 on the phase II portion). If an additional 3 patients needed to be treated in the initial phase I cohort this could potentially increase to a maximum enrollment of 47.

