Dose escalation to the 75 mg/m² dose of doxorubicin will be contingent upon acceptable safety data following the combination of Pembrolizumab and doxorubicin at the 45 mg/m² dosing. If only one of the six patients develops a DLT, a DSMB will meet prior to dose escalation to review the specific nature of the toxicity and determine if any protocol modifications are necessary prior to proceeding with the dose escalation. If there is no DLT among the first three patients, the trial may proceed immediately to the 75 mg/m² once the third patient receives cycle three (the second cycle including both Pembrolizumab and doxorubicin) without DSMB review.

As was done in the previous cohort, the second patient at the 75 mg/m² dose will not start treatment until 10 days after the first patient has received the combination of Pembrolizumab and doxorubicin at the 75 mg/m² dose level. If the first patient treated has a DLT, a DSMB will meet prior to treatment of the second patient. If two of the first six patients treated using 75 mg/m² doxorubicin develop a DLT, the phase II extension will occur using the 45 mg/m² dosing. The DSMB will meet prior to the phase II expansion. After this, the DSMB will continue to meet at least every six months while the study is enrolling.

[figure not shown]
During the dose escalation period of the trial (up to the first six patients at each dose level), patients will be monitored for 4 hours in the clinical trials unit after receiving their first infusion with the drug combination; monitoring is not required for the Cycle 1 dose of single agent pembrolizumab. After this first combination dose, patients may leave the infusion center immediately after receiving their infusions.

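### Section 5.2.1.3 both requires doxorubicin reduction after grade 3 febrile neutropenia and leaves it to discretion, and its named dose steps fit only a 75 mg/m² start

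*Combined protocol and SAP*

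**What the plan says.** All the reduction rules at issue stand in one paragraph of section 5.2.1.3.

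- First rule for febrile neutropenia: "If a patient has a grade 3 febrile neutropenia, doxorubicin should be reduced to approximately 75% of the previous dose", with the steps in brackets: "first to 60mg/m² then to 45 mg/m²".
- Next sentence: "Dose reductions of doxorubicin are also required for patients having Grade 4 neutropenia lasting more than 1 week".
- Second rule for febrile neutropenia: "For patients with grade 3 febrile neutropenia or grade 4 neutropenia without fever lasting less than a week, dose reduction may be made", and the decision belongs to the physician: "dose reduction may be made at the discretion of the treating physician".
- Limit, in the following paragraph: "Patients may not have more than 2 dose reductions of doxorubicin". It does not distinguish between starting doses.

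Two starting doses are in use. Section 2.1 says: "The Phase I stage will evaluate two dose levels of doxorubicin (45 and 75 mg/m²) combined with Pembrolizumab". Section 2.5 adds that, if two of the first six patients at 75 mg/m² have a dose limiting toxicity (DLT), "the phase II extension will occur using the 45 mg/m"² level.

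**The concern.** A dose modification rule should lead two investigators with the same patient to the same action, or state openly that the action is optional. Here the same event at the same grade is both directed and optional within three sentences. The next dose then depends on which sentence the physician applies, and neither choice can be recorded as a deviation.

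Safety and tolerability of the combination is a primary objective (section 3.1.1). If handling of a foreseen toxicity varies without a rule, the tolerability data and the doxorubicin exposure behind them become harder to interpret.

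The second issue is that the bracketed steps were evidently written for a patient starting at 75 mg/m², while the trial also starts patients at 45 mg/m².

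**Working it through.** **1. Is the first rule mandatory?** *Should* alone could be read as advice. The next sentence, on grade 4 neutropenia lasting more than a week, says that reductions are *also* required. That wording makes sense only if the reduction just described is required too.

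**2. Can the later sentence be read so that the conflict disappears?**

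- The words on absence of fever cannot apply to febrile neutropenia, so they do not narrow that half of the sentence.
- The limit of less than a week may apply to grade 4 neutropenia only. Then all grade 3 febrile neutropenia falls under both rules.
- If the limit is stretched to cover both events, a short febrile episode still falls under both rules, because the first rule has no duration limit.

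**3. Does another section decide?**

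- Section 5.2.1.1 gives the physician discretion where the protocol does not require an adjustment. Whether it does is the question in dispute.
- Section 2.3 only refers the reader to section 5.2.

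**4. Size of the divergence after a first event, 75 mg/m² start.**

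- First rule, first named step: 60 mg/m².
- Later sentence, discretion not used: 75 mg/m².
- Difference: (75 − 60) / 75 = 0.20, or 20% of the dose.
- The first reading uses one of the two permitted reductions; the second uses none.

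**5. The named steps against each starting dose** (step divided by previous dose).

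| Start | First step | Second step | Reading |
|---|---|---|---|
| 75 mg/m² | 60/75 = 80% | 45/60 = 75% | fits a reduction to roughly 75% |
| 45 mg/m² | 60 is above the starting dose | 45/45 = 100% | neither is a reduction |

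Exact 75% steps from 75 mg/m² would be 0.75 × 75 = 56.25 and 0.75 × 56.25 = 42.19 mg/m², so the named steps are rounded versions of the percentage. The plan's own figures are therefore reproduced for a 75 mg/m² start.

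From 45 mg/m² the percentage alone gives 0.75 × 45 = 33.75 and 0.75 × 33.75 = 25.31 mg/m². Neither level is named in the documents. These figures only show the gap and are not a proposal.

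**6. Who starts at 45 mg/m².** Phase I: 3 patients, or 6 if the cohort is expanded (sections 2.5 and 8.2). Phase II: up to 35 patients, but only if the 75 mg/m² level fails on DLTs. The reduction rule bites only for those among them who have a triggering event.

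**The case against.** The best defence is that the conflict sits in one paragraph, may be a drafting slip, and is buffered. Doxorubicin is held for low neutrophils or platelets whichever sentence is followed, mid-cycle bloods are taken 10 to 14 days after each infusion (section 5.2.1.4), and growth factor is allowed except in the first combination cycle of phase I (section 2.3). These safeguards are real and limit the safety consequence. They do not say which sentence governs the next dose, and the documents do not show which sentence, if either, is the slip.

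On the 45 mg/m² level, the defence is that the operative rule is relative to the previous dose and so applies from any start, with the brackets merely spelling it out for 75 mg/m². This largely stands: the level is not without a rule. What is left is that the only named steps do not fit it, and the text does not say how the percentage and the allowance of two reductions work there.

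A reader might infer four stronger points, which the documents do not support:

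- *The percentage and the steps disagree (80% against 75%).* The text says approximately, and steps of 80% and 75% fit that.
- *The protocol directs a 45 mg/m² patient to 60 mg/m².* That reads a sentence ordering a reduction as ordering an increase.
- *The whole 45 mg/m² cohort is affected.* Only patients with a triggering event are.
- *The conflict changes phase I DLT counts.* A reduction is not itself a DLT. The discontinuation that section 5.2.1.3 ties to reductions needs cytopenias of more than 21 days after a second reduction. With three-week cycles and at most one reduction per cycle, the second reduction comes no earlier than week 6 after the first combination dose, and more than 21 further days ends after week 9. That is outside the six-week window of section 2.5 and the one-cycle window of section 8.2.

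**Conclusion.** The point holds, as an internal contradiction in an operative treatment rule. For grade 3 febrile neutropenia the reduction is required by one sentence and optional by another, and nothing elsewhere resolves it. At a first event from a 75 mg/m² start the text permits next doses that differ by 20%. The named steps fit only that start. For patients starting at 45 mg/m² they are not reductions.

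The 20% figure assumes that the first rule is applied through its named first step and that a physician using the discretionary sentence chooses not to reduce. The documents give no rate of febrile neutropenia, so the number of patients affected cannot be stated. No effect on the objective response rate has been shown. The sample size, alpha and power of the two-stage design do not depend on this paragraph.

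**What to change.** Amend section 5.2.1.3 in two places. First, reconcile the febrile neutropenia sentences so that a single rule applies to the event, including any duration limit if one is intended. Second, reconcile the named steps with the 45 mg/m² starting level, and state how the percentage rule and the limit of two reductions apply to patients who start there. Which rule and which doses to use is for the sponsor to decide.

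The cost is a wording amendment to one section. No design parameter, visit or analysis changes.
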